### 8.4 Secondary Efficacy Evaluation

#### 8.4.1 16-Hour Tracer Infusion

A 16-hour tracer infusion will be performed after 28 days of treatment. The blood draw schedule during the tracer infusion is documented in [Table 2](#) in [Section 3.7](#) of the protocol. Based on the blood draws the values for the following lab tests will be obtained:

- Endogenous Glucose Production (glucose that is produced by the liver which has the tracer attached),
- Key metabolites ( $\beta$ -hydroxybutyrate, acetoacetate, lactate, pyruvate, FFA, glycerol), and
- Key hormones (insulin, C-peptide, glucagon).

For each of the lab tests, the following parameters will be derived (as appropriate):

- $AUC_{(0-16)}$ ,
- $AUC_{(0-2)}$ ,  $AUC_{(0-4)}$ ,  $AUC_{(0-8)}$ ,  $AUC_{(0-12)}$ ,
- $AUC_{(2-16)}$ ,  $AUC_{(4-16)}$ ,  $AUC_{(8-16)}$ ,  $AUC_{(12-16)}$ ,

- $C_{\max}$  (endogenous glucose production only),
- $T_{\max}$  (endogenous glucose production only), and
- $T_{\text{lag}}$  (endogenous glucose production only).

Each of these parameters for each of the tests will be analyzed using an Analysis of Variance model with treatment as the main effect.

#### **8.4.2 Hemoglobin A1c (HbA1c)**

Hemoglobin A1c will be collected prior to dosing and after 28 days of dosing. This parameter will be analyzed using an Analysis of Covariance model with treatment as the main effect and baseline value as the covariate.

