Primary Endpoint	1. Difference in endogenous glucose production between active and placebo as measured by the glucose with tracer attached using AUC (0-16) as the primary parameter.

Secondary Endpoints	

1. Mean changes in HbA1c from baseline to Day 29 of the treatment period.

2. Mean changes plasma glucose levels from baseline to Day 29 of the treatment period.

3. Mean changes in ketones from baseline to Day 29 of the treatment period.

4. Mean Changes in FFA from baseline to Day 29 of the treatment period.

5. Mean change in TC, LDLC, HDLC and TG from baseline to Day 29 of the treatment period.

6a. Difference in endogenous glucose production between active and placebo as measured by the glucose with tracer attached using other parameters including, but not limited to:

a. AUC(0-2), AUC(0-4), AUC(0-8), AUC(0-12),

b. AUC(2-16), AUC(4-16), AUC(8-16), AUC(12-16),

c. Cmax,

d. Tmax, and

e. Tlag.

6b. Difference in metabolites (<math>\beta</math>-hydroxybutyrate, acetoacetate, lactate, pyruvate, FFA, glycerol) and hormones (insulin, C-peptide, glucagon) between active and placebo using the same AUC intervals as endogenous glucose production.

7. Safety assessed by adverse event reporting including adverse events of special significance such as hypoglycemia.

Duration of Participation	Subjects will be evaluated for participation in the study during a 1 to 3-week Screening period. Following Screening, eligible subjects will enter a 4-week double blind treatment period.

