
#### 3.2 Screening/Visit 0 (Week -3 to -1, Day -21 to -7)

At the Screening Visit (Visit 0), potential subjects will be given a detailed oral presentation describing the nature, purpose, risks, and requirements of the study and will receive detailed written information. Subjects will be given ample time to consider participation and ask questions which will be adequately addressed by site personnel.

Once the subject is satisfied that he/she is willing to participate in the study, he/she will be asked to sign the study informed consent form (ICF) (refer to [Section 11.2.4](#) for further detail regarding the ICF). The investigational site personnel obtaining written consent from the subject will also sign the form to confirm consent has been obtained.

Once signed, the Investigator will retain the original ICF for the subject's study records and provide the subject with a signed copy. The investigator will verify that informed consent has been obtained from each subject prior to enrollment into the study and prior to the subject undergoing any study-related procedures.

Subjects will report to the clinic in morning following a 10-hour fast. Screening activities after obtaining informed consent will be conducted and consist of the following:

- Demographics (sex, age, race and ethnicity);
- Completion of medical and social history, including tobacco, alcohol, caffeine and drug use;
- Review of prior and current medications and supplements;
- Review of inclusion and exclusion criteria;
- Physical examination;
- 12-lead electrocardiogram (ECG);
- Measurement of height, weight and BMI;
- Measurement of vital signs (SBP/DBP and heart rate);
- Collection of fasted blood and urine samples for clinical safety labs:
  - Hematology, serum chemistry and urinalysis (see [Section 6.1.5.1](#) for list of tests);
  - HbA1c;
  - Urine drug screen;
  - Serum pregnancy test (women of childbearing potential/WCBP only);
- Breathalyzer;
- Blood plasma sample will be collected for the assessment of plasma glucose, metabolites and hormones listed in the footnote of [Table 2](#);
- Remind subjects to arrive fasting for Visit 1 in 2 weeks.

For subjects who meet eligibility criteria based on the Screening assessments, instruction will be provided on the following:

- the use of adequate contraceptive methods (see [Section 4.1](#)) for the duration of the study (Screening (Visit 0) through Visit 3);

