#### **3.3.1 Visit 1 (Week 0, Day 0)**

Subjects will report to the clinic in morning following a 10-hour fast. At Visit 1, the following procedures will be performed:

- Review of inclusion and exclusion criteria;
- Review of prior and current medications and supplements;
- Measurement of vital signs (SBP/DBP and heart rate);
- Measurement of weight;
- Breathalyzer;
- Subjects will be randomized to either ORMD-0801 (8 mg) or placebo. Subjects will be instructed to dose twice a day. Doses will occur at 45 minutes ( $\pm$  15 minutes) before breakfast and no later than 10 AM each morning, and at bedtime (@ 8 PM  $\pm$  120 minutes) each night, and no sooner than 1 hour after dinner;
- Study medication will be dispensed;
- Blood sample will be collected to measure HbA1c;
- AEs/SAEs assessment;
- Remind subjects to arrive fasting for Visit 2 in 2 weeks.

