### 3.4 Tracer Infusion

#### 3.4.1 Visit 3 (Week 4, Day 28)

Subjects will report to the clinic in morning following a 10-hour fast. At Visit 3 (Day 28), the following procedures will be performed:

- Admission to the CRU (8 AM  $\pm$  120 minutes);
- Review of prior and current medications and supplements;
- Measurement of vital signs (SBP/DBP and heart rate);
- Measurement of weight;
- Breathalyzer;
- Urine pregnancy test (women of childbearing potential/WCBP only);
- Fasting blood sample will be collected to measure HbA1c;
- Study medication will be collected, and compliance will be reviewed;
- Subjects will be provided with a standard breakfast, lunch and dinner. The morning dose will be administered 45 minutes ( $\pm$  15 minutes) before breakfast and no later than 10 AM, in-clinic. A light standardized dinner meal will be provided at 6 PM  $\pm$  30 minutes.
- Subjects will be dosed in-clinic with either ORMD-0801 (8 mg) or placebo (@ 8 PM  $\pm$  60 minutes) and started on a 16-hour infusion of [6,6-H2]-glucose tracer immediately following dosing;
- Blood samples will be collected to measure endogenous glucose (tracer attached), plasma glucose, metabolites and hormones for the duration of the infusion. Blood samples will be drawn at baseline (pre-infusion), 45, 90, 120 and 150 minutes, and 3 and 4 hours (see blood draw schedule in [Table 2](#)). Subjects will be required to remain fasting from the evening of Day 28 (following dinner) until the end of the infusion;
- A backup blood sample will be collected at baseline (pre-infusion);
- AEs/SAEs assessment.

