### 6.2.2 Hemoglobin A1c (HbA1c)

Hemoglobin A1c will be collected at every visit.

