#### **8.5.3 Laboratory Evaluations**

Individual clinical safety lab (hematology, serum chemistry, and urinalysis) values will be listed by visit and summarized using descriptive statistics as appropriate (i.e., mean, median, range, and standard deviation for continuous data and frequency for categorical data). Individual change from baseline (Screening) in laboratory values will be calculated and summarized descriptively. A clinically significant change from baseline will be recorded as an AE if deemed appropriate by the Investigator.

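### HbA1c is drawn twice before dosing and twice at Week 4, but the endpoint uses only Day 29, Day 28 has no stated use, and the baseline covariate is not tied to a visit

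*Combined protocol and SAP*

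**What the plan says.** Section 6.2.2 states: "Hemoglobin A1c will be collected at every visit". The schedule agrees. HbA1c is listed at Screening (Section 3.2, 7 to 21 days before Day 0), at Visit 1 on Day 0 (Section 3.3.1: "Blood sample will be collected to measure HbA1c"), at Visit 2 on Day 14, on Day 28 (Section 3.4.1: "Fasting blood sample will be collected to measure HbA1c") and again, fasting, on Day 29 (Section 3.5.1). Table 1 marks all five.

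The first secondary endpoint, in the Synopsis and Section 2, is "Mean changes in HbA1c from baseline to Day 29 of the treatment period". The matching objective refers to Week 4.

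Section 8.4.2 says "Hemoglobin A1c will be collected prior to dosing and after 28 days of dosing" and specifies an ANCOVA with "treatment as the main effect and baseline value as the covariate". It names no visit for the baseline and gives no rule for choosing or combining samples. Sections 8.4.3 to 8.4.5, by contrast, say which post-treatment value is analysed.

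The one place that ties a laboratory baseline to a visit is Section 8.5.3: "Individual change from baseline (Screening) in laboratory values will be calculated and summarized descriptively". That paragraph covers the clinical safety laboratories: hematology, serum chemistry and urinalysis.

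**The concern.** Four weeks is a short exposure for HbA1c, and the trial has about 40 subjects, a number that Section 8.2 says was not chosen on statistical grounds. Measurement noise in one sample at each end goes straight into the residual variance of the ANCOVA. A second sample at each end is already scheduled, yet the analysis as written does nothing with Day 28 and leaves open what happens to the second pre-dose value.

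Two practical consequences follow. With two eligible pre-dose values and no rule, the choice of covariate could be made after the data are seen. And because Section 8.5.8 allows no substitution of missing data, a subject whose Day 29 sample is lost has no endpoint value, even with a valid HbA1c from the day before.

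**Working it through.** There is no figure in the plan to reproduce: it gives no HbA1c standard deviation, effect size, power or alpha.

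**Inputs**

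- From the documents: about 40 subjects in two arms (Section 5.2), two pre-dose and two Week 4 HbA1c samples, and an ANCOVA with one baseline covariate.
- Assumed: 1:1 allocation (20 per arm; the ratio is not stated); SD of the true baseline value *sT* 0.7 to 0.9 percentage points; error SD per sample *e* 0.1 to 0.3; SD of the true 4-week change *sc* 0.3 to 0.5; no true change between Screening and Visit 1.

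**Formula.** With *kb* baseline samples and *kf* Week 4 samples averaged, and correlation *ρ* between the two Week 4 errors:

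- Vx = sT² + e²/kb
- Vy = sT² + sc² + Ve, where Ve = e² for one Week 4 sample and e²(1 + ρ)/2 for the mean of two
- residual variance = Vy − sT⁴/Vx
- SE of the treatment difference = √(2 × residual variance / 20)

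**Worked example** (sT = 0.8, e = 0.20, sc = 0.3; sT² = 0.64, sT⁴ = 0.4096)

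- One sample at each end: 0.77 − 0.4096/0.68 = 0.1676; SE = 0.129.
- Two at each end, independent errors: 0.75 − 0.4096/0.66 = 0.1294; SE = 0.114. Variance falls 23%, SE 12%.
- Two at each end, ρ = 0.5: 0.76 − 0.4096/0.66 = 0.1394; SE = 0.118. Variance falls 17%, SE 9%.

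**Range** (sT = 0.9; results at 0.7 are close)

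| e | sc | SE, one/one | SE, two/two, independent | SE, two/two, ρ = 0.5 | SE reduction |
|---|---|---|---|---|---|
| 0.1 | 0.5 | 0.164 | 0.161 | 0.162 | 1.9% / 1.4% |
| 0.1 | 0.3 | 0.105 | 0.100 | 0.101 | 4.6% / 3.4% |
| 0.2 | 0.5 | 0.181 | 0.170 | 0.173 | 6.1% / 4.5% |
| 0.2 | 0.3 | 0.130 | 0.114 | 0.118 | 12.2% / 8.9% |
| 0.3 | 0.5 | 0.205 | 0.184 | 0.190 | 10.4% / 7.5% |
| 0.3 | 0.3 | 0.162 | 0.133 | 0.142 | 17.5% / 12.4% |

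Over both values of sT, the SE falls by 1.8% to 17.5% with independent errors and by 1.4% to 12.4% with ρ = 0.5. With independent errors this is equivalent to analysing about 41.5 to 59 subjects instead of 40. Averaging the baseline alone gives 0.9% to 7.6%.

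**Selection on HbA1c.** A simulation (5,000 trials per setting; true HbA1c mean 8.3, sT 0.9, sc 0.4, e 0.1 to 0.3) admitted subjects whose Screening value lay between 7.5% and 11%. The Visit 1 mean was lower than the Screening mean by only 0.004 to 0.032 points. With no true effect, the estimated ANCOVA contrast averaged at most 0.0035, which is within simulation error (Monte Carlo SE about 0.002 to 0.003). Using Screening or Visit 1 as the single covariate gave nearly the same SE (0.154 for both at e = 0.2).

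**The case against.** One Day 29 value with a baseline covariate is a valid analysis, and HbA1c is a secondary endpoint. Section 8 defers further detail to a statistical analysis plan, and no separate SAP text is in the documents reviewed; the rule for repeat samples could be set there. Every variance input is assumed. The gain is smaller than a variance percentage suggests, smaller again if errors a day apart are correlated, and would shrink further if HbA1c drifts between Screening and Visit 1. All of this stands, and it limits the size of the point. It does not explain why the stated endpoint leaves out a Week 4 sample that is already scheduled.

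A reader might infer more: that the plan fixes the HbA1c baseline at Screening and so discards Visit 1. The documents do not support that. The reference to Screening in Section 8.5.3 belongs to the safety laboratories. HbA1c appears beside those tests in the Screening list of Section 3.2, as do the urine drug screen and pregnancy test, but it is absent from the test lists in Section 6.1.5.1 and is handled as an efficacy measure in Sections 6.2.2 and 8.4.2. Its baseline is undefined: Screening, Visit 1 or their mean would all fit Section 8.4.2.

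A reader might also infer that selection on Screening HbA1c biases the treatment comparison. It does not. Both arms are selected in the same way before randomization, so regression to the mean affects within-arm changes and not the randomized contrast, as the simulation shows.

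**Conclusion.** The point holds as a modest, nearly free gain in precision, together with a gap in specification. The endpoint uses only Day 29, Day 28 has no stated role, and the baseline covariate is not tied to a visit. Under the assumed ranges, averaging at both ends lowered the SE in every setting: by about 2% to 17% with independent errors, and by about 1% to 12% with a Day 28/Day 29 error correlation of 0.5. If the error SD is near 0.1 the benefit is slight (at most 4.6%). Nothing here shows bias in the planned ANCOVA, and the primary endogenous glucose production analysis is unaffected.

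**What to change.** Before unblinding, specify in Section 8.4.2 (and carry into the SAP):

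- the baseline covariate is the mean of the Screening and Visit 1 HbA1c values;
- the Week 4 outcome is the mean of the Day 28 and Day 29 values;
- if one of a pair is missing, the other is used. Write this as part of the definition, so that it does not conflict with the no-substitution rule in Section 8.5.8.

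The ANCOVA stays as planned. For HbA1c only, change the end point of the first secondary endpoint in the Synopsis and Section 2 from Day 29 to Week 4 (mean of Day 28 and Day 29). The objective already refers to Week 4 and needs no change.

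The cost is a short definition and a minor edit to the endpoint wording in two places. No extra blood, visits or assays are needed.

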#### **8.4.3 Plasma Glucose Levels**

Plasma glucose levels will be collected prior to dosing and after 28 days of dosing. The plasma glucose levels collected after the 16-hour infusion period is complete, is the value that will be analyzed for this test. This parameter will be analyzed using an Analysis of Covariance model with treatment as the main effect and baseline value as the covariate.

#### **8.4.4 Ketones and Free Fatty Acids**

Ketones and free fatty acid levels will be collected prior to dosing and after 28 days of dosing. The values collected after the 16-hour infusion period is complete, are the values that will be analyzed for these tests. These parameters will be analyzed using an Analysis of Covariance model with treatment as the main effect and baseline value as the covariate.

#### **8.4.5 Lipids (Total Cholesterol, LDL Cholesterol, HDL Cholesterol and Triglycerides)**

Lipids will be collected prior to dosing and after 28 days of dosing. The values collected after the 16 hour infusion period is complete, are the values that will be analyzed for these tests. These parameters will be analyzed using an Analysis of Covariance model with treatment as the main effect and baseline value as the covariate.

### **8.5 Safety Evaluation**

#### **8.5.1 Safety Population**

All randomized subjects who receive at least one dose of study treatment will be included in the safety analysis population.

#### **8.5.2 Adverse Events**

AEs will be coded using the most current version of MedDRA.

The incidence of TEAEs will be tabulated by MedDRA preferred term, system organ class, treatment group, severity, and assigned relationship to study treatment. The incidence for each TEAE will be provided as the total number of subjects that experienced the TEAE, as well as the

percentage of the population that this represents. If a TEAE is reported more than once for a given subject, the greatest severity and the worst-case attribution will be presented in the summary tables.

TEAEs will be listed for individual subjects, along with information regarding onset and end dates, onset time where available, severity, seriousness, relationship to study treatment, action taken, and outcome. A similar listing will be prepared for the pretreatment AEs.

TEAEs that lead to withdrawal from the study will be separately listed and summarized.

Descriptive statistics will be generated as appropriate (i.e., frequency for categorical data). Inferential statistical analysis comparing the AE data between active and placebo is not planned.

#### **8.5.3 Laboratory Evaluations**

Individual clinical safety lab (hematology, serum chemistry, and urinalysis) values will be listed by visit and summarized using descriptive statistics as appropriate (i.e., mean, median, range, and standard deviation for continuous data and frequency for categorical data). Individual change from baseline (Screening) in laboratory values will be calculated and summarized descriptively. A clinically significant change from baseline will be recorded as an AE if deemed appropriate by the Investigator.

#### **8.5.4 Vital Signs**

Individual vital sign measurements (height, weight, seated SBP/DBP, and heart rate) will be listed by measurement time and summarized using descriptive statistics as appropriate (i.e., mean, median, range, and standard deviation). Individual change from baseline in vital sign measurements will be calculated and summarized descriptively. A clinically significant change from baseline will be recorded as a TEAE if deemed appropriate by the Investigator.

#### **8.5.5 12-lead ECG**

Individual 12-lead ECG assessments are only collected as screening and will be listed.

#### **8.5.6 Physical Examination**

Individual physical examination findings will be listed by visit. A clinically significant change from baseline will be recorded as an AE if deemed appropriate by the Investigator.

#### **8.5.7 Prior and Concomitant Medications and Supplements**

Medications and supplements will be coded using the most current version of the WHO Drug Reference List, which employs the Anatomical Therapeutic Chemical classification system. Concomitant medications and supplements will be listed for individual subjects. A similar listing will be prepared for prior medications and supplements stopped within 30 days prior to the first dose of study treatment. The incidence of these prior and concomitant medications and supplements will be summarized.

### 8.5.8 Handling of Missing, Unused, or Spurious Data

Descriptive statistics and listings will be provided for all data. No substitution of missing data will be used in any calculations. Data points that appear to be spurious will be investigated and will not be excluded from the listings. Influential cases will be handled in an appropriate statistical manner.

## **9 DATA MANAGEMENT**

### **9.1 Data Collection**

All data required by the study protocol will be collected in a validated database according to the CRO's SOPs.

#### **9.1.1 Electronic Data Capture**

Data from the source documents will be entered into the EDC system by authorized Investigational Site personnel. Data Management staff, using both electronic and manual checks, will systematically check the data. Errors or omissions will result in queries (which can be issued by the Study Monitor or Data Management staff), which will be presented to the Investigational Site within the EDC system. The Investigational Site will resolve the queries within the EDC system. The Study Monitor and Data Management staff will review the responses as part of the query resolution process. The EDC system will track the queries with the corresponding responses.

Medications and supplements entered into the database will be coded in the EDC system using the WHO Drug Reference List, which employs the Anatomical Therapeutic Chemical classification system. AEs and Medical History will be coded in the EDC system using MedDRA terminology.

Laboratory samples will be processed by appropriate laboratories. Results will be reported to Integrium and imported into the database.

### **9.2 Quality Assurance and Database Lock**

A 100% critical variable review of all key safety and secondary endpoint data in the database will be performed. Following this review, a data quality control audit or a random sample equal to 10% of subjects, with a minimum of 5 subjects will be performed.

When the database has been declared to be complete and accurate, the database will be locked. Any changes to the database after that time can only be made by joint written agreement between the Sponsor, the Investigator, Integrium, and the study biostatistician.

## **10 AMENDMENTS/MODIFICATIONS OF THIS PROTOCOL**

The Investigator will ensure that the study is conducted in accordance with the procedures and evaluations described in this protocol. As the study progresses it may become necessary to change or modify parts of the protocol. The Sponsor or designee is responsible for submitting protocol amendments to the appropriate government regulatory authorities. The Investigator is responsible for submitting protocol amendments to the appropriate IRB. Approval by the IRB must be obtained before changes are implemented.

When an emergency occurs that requires a departure from the protocol for an individual, a departure will be only for that subject. The Investigator or other physician in attendance in such an emergency will, if circumstances and time permit, contact the Medical Monitor immediately by telephone. Such contacts will be made as soon as possible to permit a decision as to whether or not the subject (for whom the departure from protocol was affected) is to continue in the study. The eCRF and source documents will completely describe the departure from the protocol and state the

reasons for such departure. In addition, the IRB will be notified in writing of such departure from protocol.

